#### 4.1.3 Research studies

- Biospecimens will be collected for research to identify biomarkers of response, understand the mechanism of action of the treatment, and investigate the biology of RRP.

- Research studies will be considered exploratory analyses and will include all or some of the following: assessment of PD-L1 expression by papillomas and papilloma-infiltrating immune cells, testing of papillomas and normal appearing mucosa for HPV, and evaluation of papilloma-infiltrating T cell responses against HPV antigens.
- Testing of papilloma-infiltrating T cells and peripheral blood T cells for recognition of HPV antigens [25].

#### Generation and isolation of T cells

Papilloma-infiltrating T cells will be generated from papilloma biopsy specimens by culture of 2 mm tissue fragments in culture media with IL-2. Lymphocyte cultures will be split when confluent and cryopreserved when sufficient cells have been generated. Flow cytometry may be performed to assess the lymphocyte populations using markers such as CD3, CD4, CD8, and CD56 to assess lymphocyte subtypes. T cells will be isolated from peripheral blood samples by magnetic bead separation using standard techniques from commercially available kits (Miltenyi or similar).

#### HPV-specific T cell response assays

Target cells for assays measuring HPV-specific T cells responses will be autologous immature dendritic cells (DCs) generated from apheresis samples. The DCs will be loaded with pools of overlapping peptides spanning each of the viral antigens encoded by HPV. Reactivity against each antigen will be assessed separately. Immunological assays may consist of interferon-gamma ELISPOT, interferon-gamma production as determined by ELISA, 4-1BB upregulation, and or intracellular cytokine production as described previously [25].

#### HPV detection and genotyping

Testing will be performed by [name] laboratory using PCR-based type-specific HPV detection and quantification assays [25].

#### 4.1.4 Co-Enrollment on 16C0061 / Biobanking

Samples from patients may be transferred to protocol 16C0061 for biobanking of specimens if the patient has consented to that study.

#### 4.1.5 Sample Storage, Tracking and Disposition

##### Preclinical Development and Clinical Monitoring Facility

- Samples will be archived by the ETIB Preclinical Development and Clinical Monitoring Facility (PDCMF). All data associated with archived clinical research samples is entered into the ETIB PDCMF's Microsoft Excel databases on frozen cells and plasma. These databases are stored on the NCI group drive in the ETIB 'PRECLINSERVICE' folder. Access to this folder is limited to PDCMF staff and ETIB clinical staff, requiring individual login and password. All staff in the PDCMF laboratory receives annually updated NIH/CIT training and maintains standards of computer security.
- The data recorded for each sample includes the patient ID, trial name/protocol number, date drawn, treatment cycle/post-transplant time point, cell source (e.g. peripheral blood, lymph apheresis, mobilized peripheral blood stem cells, marrow, urine, skin or oral biopsy) as well as box and freezer location. Patient demographics that correlate treatment outcomes and therapies with the samples can be obtained only through the NCI/ETIB clinical records. As of January 2007, all newly received samples receive a unique bar code number, which is included in the sample record in the PDCMF database. Only this bar code is recorded on the sample vial and the vials will not be traceable back to patients without authorized access to the PDCMF database. All non-coded samples previously archived will be stripped of identifiers prior to distribution for any use other than as a primary objective of the protocol under which they were collected.
- Samples are stored in locked freezers. All samples will be labeled solely with a bar code (which includes the date, and serially determined individual sample identifier). The key will be available to a restricted number of ETIB investigators and associate investigators on the protocol. Coded samples will be stored frozen at -20°, -80° or liquid nitrogen vapor phase according to the stability requirements under the restricted control of the PDCMF Facility of ETIB.
- Access to samples from a protocol for research purposes will be by permission of the Principal Investigator of that protocol in order to be used (1) for research purposes associated with protocol objectives for which the samples were collected, or (2) for a new research activity following submission and IRB approval of a new protocol and consent, or (3) for use only as unlinked or coded samples under the OHSRP Exemption Form guidelines stipulating that the activity is exempt from IRB review. Unused samples must be returned to the PDCMF laboratory.

- Samples, and associated data, will be stored permanently unless the patient withdraws consent. If researchers have samples remaining once they have completed all studies associated with the protocol, they must be returned to the PDCMF laboratory.
- These freezers are located onsite at the PDCMF laboratory (12C216) or in ETIB common equipment space (CRC/3-3273).

#### 4.1.5.1 [name] laboratory

- Samples may be transferred from Preclinical Development and Clinical Monitoring Facility to the [name] laboratory for the research studies indicated in [4.1.3](#).
- Samples transferred to the [name] laboratory will be barcoded and tracked with LabMatrix.
- Laboratory research data will be stored on the NCI secure server in the [name] laboratory folder with secure access by laboratory personnel only.

#### 4.1.6 Protocol Completion/Sample Destruction

- Once research objectives for the protocol are achieved, researchers can request access to remaining samples, providing they have both approval of the Principal Investigator of the original protocol under which the samples or data were collected and either an IRB approved protocol and patient consent or the OHSRP Exemption Form stipulating that the activity is exempt from IRB review.
- The PDCMF staff will report to the Principal Investigators any destroyed samples, if samples become unsalvageable because of environmental factors (ex. broken freezer or lack of dry ice in a shipping container), lost in transit between facilities or misplaced by a researcher.

The PI will record any loss or unanticipated destruction of samples as a deviation. Reporting will be per the requirements of section [6.2](#).

## 5 DATA COLLECTION AND EVALUATION

### 5.1 DATA COLLECTION

The PI will be responsible for overseeing entry of data into an in-house password protected electronic system and ensuring data accuracy, consistency and timeliness. The principal investigator, associate investigators/research nurses and/or a contracted data manager will assist with the data management efforts. All data obtained during the conduct of the protocol will be kept in secure network drives or in approved alternative sites that comply with NIH security standards. Primary and final analyzed data will have identifiers so that research data can be attributed to an individual human subject participant.

All adverse events, including clinically significant abnormal findings on laboratory evaluations, regardless of severity, will be followed until return to baseline or stabilization of event. Patients will be followed for adverse events for minimum of 30 days after removal from study treatment or until off-study, whichever comes first.

An abnormal laboratory value will be recorded in the database as an AE **only** if the laboratory abnormality is characterized by any of the following:

- Results in discontinuation from the study
- Is associated with clinical signs or symptoms
- Requires treatment or any other therapeutic intervention
- Is associated with death or another serious adverse event, including hospitalization.
- Is judged by the Investigator to be of significant clinical impact
- If any abnormal laboratory result is considered clinically significant, the investigator will provide details about the action taken with respect to the test drug and about the patient's outcome.

**End of study procedures:** Data will be stored according to HHS, FDA regulations and NIH Intramural Records Retention Schedule as applicable.

**Loss or destruction of data:** Should we become aware that a major breach in our plan to protect subject confidentiality and trial data has occurred, this will be reported expeditiously per requirements in section **6.2.1**.

#### 5.1.1 Concomitant medications recording:

Only medications used to treat adverse events related to the study medication will be recorded in the data base.

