#### 1.1.2 Secondary Objectives

- Exploratory analyses to assess:
  - PD-L1 expression as a potential biomarker of response.
  - HPV type as a potential biomarker of response.
  - Induction of HPV-specific T cells responses.
  - Clearance of HPV infection from normal appearing mucosa.
- Determine the effect of treatment with avelumab on Derkey and Voice Handicap Index-10 scores.
- Determine the partial response rate for avelumab
- Determine the duration of clinical responses to avelumab

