### **1.2 BACKGROUND AND RATIONALE**

#### 1.2.1 Recurrent respiratory papillomatosis (RRP)

RRP is a rare but difficult-to-treat and sometimes fatal neoplastic disease of the aerodigestive tract. RRP is caused by infection with human papillomavirus (HPV) type 6 or 11, or more rarely type 16 [1]. Approximately 1,500 new cases of RRP are diagnosed each year in the United States [2]. RRP is classified based on age of onset as juvenile or adult. Juvenile-onset disease has an incidence of 4/100,000 and tends to have an aggressive clinical course. Adult-onset RRP has an incidence of 2-3/100,000 and tends to have a more indolent clinical course. RRP morbidity and mortality results from papilloma mass effects on the vocal cords, airways, or lungs. This may cause voice changes, stridor, airway occlusion, loss of lung volume, and/or pneumonia [3]. Repeated procedures are required to debulk and monitor the disease, which exposes patients to anesthetic and surgical risk, and emotional distress. It is estimated that the economic cost of RRP is \$150M in the United States each year [2]. Although rare (one to three percent of cases) RRP can transform into invasive squamous cell carcinoma [4]. Subsequent mortality is based upon the clinical stage of the malignancy at the time of diagnosis.

[figure not shown]
There is no cure for RRP. The mainstay of treatment is endoscopic debulking with ablation or excision of papillomatous lesions. Surgical principles dictate that, to minimize morbidity from treatment, papillomatous disease but not normal appearing epithelium is removed. It is thought that latent HPV viral particles persistent in an inactive state in the clinically-normal mucosa and subsequently become reactivated leading to RRP recurrence [5]. Patients with juvenile-onset RRP require on average 20 surgeries over their lifetime to control their disease [6]. Patients with adult-onset RRP generally require fewer interventions; nonetheless greater than 50% will require 5 or more procedures to control symptoms [7]. Adjuvant systemic therapies have been tested in clinical trials, including systemic interferon- $\alpha$  and local injection of anti-viral and antiangiogenic

agents [5]. Study results have been inconsistent, and no single adjuvant approach has been widely adopted or accepted as the standard of care.

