#### **3.6.1 Criteria for removal from protocol therapy**

Patients will be taken off treatment for the following:

- Completion of protocol therapy
- Participant requests to be withdrawn from active therapy
- The patient receives any other treatment for RRP or requires the use of any corticosteroids (> 10 mg daily prednisone equivalents) or other immunosuppressive medications.
- General or specific changes in the patient's condition render the patient unacceptable for further treatment on this study in the judgment of the investigator.
- Any Grade 3/4 drug-related adverse events with the exceptions as detailed in section 3.4.
- Disease progression
- Participant becomes pregnant

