#### 5.1.2 Collection of recurrence and subsequent treatments

The dates of disease recurrences following completion of treatment and/or debulking on this study and the dates and types of additional interventional procedures to control RRP will be recorded.

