## **9 STATISTICAL CONSIDERATIONS**

The trial will be conducted using a Simon optimal two-stage design; the objective is to rule out a 5% complete response rate ( $p_0=0.05$ ) and target a 20% complete response rate ( $p_1=0.20$ ).

The design will use  $\alpha=0.10$  (10% chance of accepting a poor agent) and  $\beta=.10$  (corresponding to 90% power--and 10% chance of incorrectly rejecting a promising agent).

The first stage of accrual will consist of 12 evaluable patients. If 0/12 has a complete clinical response, then no further patients would be enrolled to that cohort. Should 1 or more patients in the first 12 have a complete response, then accrual would continue until a total of 37 evaluable patients have enrolled. If there are 1 to 3 complete responses in 37 patients, this would be considered unacceptably low, while if 4 or more patients have complete responses in 37 patients, then the results will be considered sufficiently promising for further evaluation. Under the null hypothesis (5% complete response rate), the probability of early termination is 54.0%.

It is anticipated that up to 2 patients per month may enroll onto this trial; thus, up to 2 years may be required to complete accrual. The trial would require up to 37 total evaluable patients; the accrual ceiling will be set at 40 patients to allow for a small number of inevaluable patients.

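### An RRP drug started by a responder before recurrence need not enter the database, so duration of response to avelumab can include time on another drug

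*Combined protocol and SAP*

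**What the plan says.** On concomitant drugs, Section 5.1.1 is one sentence: "Only medications used to treat adverse events related to the study medication will be recorded in the data base". On what happens after study treatment, Section 5.1.2 requires recurrence dates and says that "the dates and types of additional interventional procedures to control RRP will be recorded".

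Section 3.6.1 lists among the reasons for stopping protocol therapy: "The patient receives any other treatment for RRP or requires the use of any corticosteroids" (above a stated daily dose) or other immunosuppressive medication. Section 1.2.1 shows which other RRP drugs are in view: systemic interferon and "local injection of anti-viral and antiangiogenic" agents.

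Section 1.1.2 lists as a secondary objective: "Determine the duration of clinical responses to avelumab". Section 5.2.4 runs best response from the start of treatment to progression or recurrence and does not mention a new RRP drug. Section 9 gives no estimator or censoring rule for duration.

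**The concern.** Section 5.1.1 is an explicit restriction, so a site that follows it exactly leaves out drugs given for any purpose other than a study-drug-related adverse event. If a patient in response then starts another RRP drug and stays free of recurrence, the database shows one unbroken avelumab response. The analyst can neither identify the patient nor run a sensitivity analysis.

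The protocol itself treats this as plausible. Section 1.2.3 reports that adjuvant interferon lengthened time to recurrence in the short term, though without lasting benefit. A drug that delays recurrence would lengthen the apparent duration of response.

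What is at stake is the interpretation of a secondary objective. Drug start dates are also hard to reconstruct years later, when part of the follow-up is by annual phone or email contact.

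**Working it through.** **1. What must be recorded, and for whom**

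| Source | Patients and period | What is captured | Covers an RRP drug started in response, before recurrence? |
|---|---|---|---|
| 5.1.1 | all | drugs treating study-drug-related adverse events | No |
| 5.1.2 | after treatment and/or debulking | recurrence dates; dates and types of procedures | No, unless a local injection is classed as a procedure |
| 3.3.6 and Study Calendar note r | non-responders, yearly for 2 years | recurrence and treatments received | Not these patients |
| 3.3.6 and Study Calendar note q | CR and PR, yearly contact for 3 years after the clinic visits | status, recurrence dates, interventions for recurrent disease | No, tied to recurrence |
| 3.6.2 | CR | recurrence dates, interventions for recurrent disease | No, tied to recurrence |
| 3.6.2 | no CR (so including PR) | recurrence after debulking; interventional procedures | No, procedures only |
| 3.6.1 with 2.4 | while on therapy | removal from therapy as a status update | No; the drug and its dates are not required, and therapy has ended |

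Medications are reviewed within 3 days before each dose (2.2.2.3, 3.3.1), but Section 5.1.1 keeps most of that review out of the database. The list of follow-up evaluations in 3.3.6 has an interval history and no medication review. Stopping therapy does not end follow-up, because 3.6.3 does not list it as an off-study reason.

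**2. Length of exposure**

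Responder clinic visits (3.3.6): every 6 weeks × 3, every 12 weeks × 3, every 26 weeks × 2.

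- Total: 3×6 + 3×12 + 2×26 = 18 + 36 + 52 = 106 weeks.
- Visits fall at weeks 6, 12, 18, 30, 42, 54, 80 and 106 after the last dose.
- Response is assessed 6 weeks after the first dose, or at 12 weeks after a partial response (3.1.1).
- Ratio: 106/12 ≈ 8.8 to 106/6 ≈ 17.7.

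The period in which duration can be affected is thus roughly 9 to 18 times the period in which a first CR can be affected, before counting the 3 further years of annual contact.

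Hypothetical case on that schedule: a complete responder starts an RRP drug at the week 18 visit and recurs at week 54. The record shows response to week 54. With censoring at the new drug, follow-up in response ends at week 18. The difference, 54 − 18 = 36 weeks, is invisible without the drug's start date.

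**3. The plan's own design figures**

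Section 9: "the objective is to rule out a 5% complete response rate" and "target a 20% complete response rate", with a "10% chance of accepting a poor agent"; stop at 0 of 12, promising at 4 or more of 37.

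- Early termination under the null: 0.95^12 = 0.5404, matching the stated 54.0%.
- P(promising) = Σ over x = 1 to 12 of P(X₁ = x; 12, p) × P(X₂ ≥ 4 − x; 25, p). This is 0.0935 at p = 0.05 and 0.9024 at p = 0.20, within the 0.10 limit and above the 0.90 target.

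The recording rule does not enter these figures, so no change to the design follows.

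**The case against.** The case against is substantial, and much of it stands.

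- **Much is captured.** Steroids for avelumab-related events fall inside 5.1.1. Non-responders' later treatments are documented. A local injection can reasonably be read as a procedure under 5.1.2. It would be wrong to say that RRP drugs and steroids in general are missing from the database.
- **The source record is wider than the database.** Pre-dose review, weekly calls on treatment and interval histories would often reveal another drug, and monitoring checks response against source documents. This stands, but nothing obliges the site to transfer the drug and its dates to the data that are analysed.
- **A responder usually starts another drug because disease has returned,** and that date is recorded. This is often true. The gap is confined to drugs started earlier, for maintenance or prevention.
- **Debulking at the end of treatment may disturb duration in partial responders more than any drug.** That is a separate matter and does not close this gap.

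A reader might infer two stronger claims.

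- **That unrecorded steroids could cause or prolong a response.** No section says so. Section 2.1.1.8 says that the treatment depends on an intact immune system, which points the other way.
- **That misattributed CRs are likely to reverse the 4-of-37 decision.** If a share c of patients without a CR were wrongly counted as CR, the null rate would become 0.05 + 0.95c. P(promising) would rise from 0.093 to 0.148 at c = 1% and 0.212 at c = 2%. But c is purely assumed, and any threshold rule behaves this way. The documents make a false CR difficult: a four-week washout of systemic RRP therapy (2.1.1.5), removal from therapy for other RRP treatment (3.6.1), and CR requiring an exam under anesthesia with biopsies (5.2.3.1), timed 9 to 17 days after the last dose in the Study Calendar.

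**Conclusion.** The point holds in a narrow form. Followed as written, Sections 5.1.1, 5.1.2, 3.3.6 and 3.6.2 leave an RRP-directed drug started by a responder before documented recurrence outside the required data, and no response or duration rule compensates. The consequence falls on duration of response. The primary CR endpoint is only slightly exposed, and the design is unaffected.

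The size cannot be estimated because the documents give no frequency of such drug use. The 106-week figure measures opportunity, not bias. The conclusion assumes that sites apply the restriction in 5.1.1 literally and that a systemic drug is not entered as a procedure. This is an inexpensive improvement to data collection, and it does not call the trial's main conclusion into question.

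**What to change.** Amend Section 5.1.1 so that the database also holds, with drug, dates and reason:

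- any RRP-directed drug, systemic or local;
- any systemic corticosteroid or immunosuppressant that meets the removal criterion in 3.6.1, so that the reason for removal can be traced.

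Collect these from baseline until recurrence or the end of response follow-up. Add the question to the follow-up list in 3.3.6 and to the annual contact for responders.

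In Section 9, state that any response first documented after another RRP drug will be flagged, and that duration of response will be reported with and without censoring at the start of that drug. Reporting both avoids committing to one debatable convention.

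The cost is a few extra entries per patient, in at most 40 patients. On treatment the medication review already takes place; in follow-up it is one added question. Sample size, decision rule and clinical management do not change.

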#### 5.1.2 Collection of recurrence and subsequent treatments

The dates of disease recurrences following completion of treatment and/or debulking on this study and the dates and types of additional interventional procedures to control RRP will be recorded.

#### 5.1.3 Collection of Adverse Events following surgery/procedure

Grade 1 or 2 adverse events that are clearly attributable to surgery/procedure will not be recorded.

